7.0 Vulnerable Populations

If the research involves special populations that are considered vulnerable, describe the safeguards included to protect their rights and welfare.

NOTE: You should refer to the appropriate checklists, referenced below, to ensure you have provided adequate detail regarding safeguards and protections. You do not, however, need to provide these checklists to the IRB.

7.1 *For research that involves **pregnant women**, safeguards include:*

NOTE CHECKLIST: Pregnant Women (HRP-412)

Response: We will not be using subjects from vulnerable populations

- N/A:** This research does not involve pregnant women.

7.2 *For research that involves **neonates of uncertain viability or non-viable neonates**, safeguards include:*

NOTE CHECKLISTS: Non-Viable Neonates (HRP-413), or Neonates of Uncertain Viability (HRP-414)

Response:

- N/A:** This research does not involve non-viable neonates or neonates of uncertain viability.

7.3 *For research that involves **prisoners**, safeguards include:*

NOTE CHECKLIST: Prisoners (HRP-415)

Response:

N/A: This research does not involve prisoners.

7.4 *For research that involves persons who have not attained the legal age for consent to treatments or procedures involved in the research (“children”), safeguards include:*

NOTE CHECKLIST: Children (HRP-416)

Response:

N/A: This research does not involve persons who have not attained the legal age for consent to treatments or procedures (“children”).

7.5 *For research that involves cognitively impaired adults, safeguards include:*

NOTE CHECKLIST: Cognitively Impaired Adults (HRP-417)

Response:

N/A: This research does not involve cognitively impaired adults.

7.6 *Consider if other specifically targeted populations such as students, employees of a specific firm, or educationally or economically disadvantaged persons are vulnerable. Provide information regarding their safeguards and protections, including safeguards to eliminate coercion or undue influence.*

Response: No specific populations or vulnerable groups will be targeted. All subjects enrolled in this study will be of legal adult consenting age with the ability to speak, read and interrupt the English language. Patients will have the ability to speak with the research team regarding any questions or concern they have before signing the consent. Patients are made aware that this study is voluntary and they are able to stop participating at any time they feel uncomfortable. Patients are not be pressured into participating and their clinic standard of care will remain the same if they participate or choose not to participate.

8.0 Eligibility Screening

8.1 *Describe screening procedures for determining subjects’ eligibility. Screening refers to determining if prospective participants meet inclusion and exclusion criteria.*

 *Include all relevant screening documents with your submission (e.g. screening protocol, script, questionnaire).*

Response:

After obtaining all necessary approval to conduct the study, study coordinator or investigators will conduct a prescreening phone conversation with referred or interested patients. Patients will then be schedule for a screening visit. Prospective participants will be asked to read and understand the consent and any questions they may have regarding the study will be answered. If the subject wants to participate in the study, they will be asked to sign the informed consent form. The subject’s medical history and current medications will be obtained as well as their blood pressure and vitals. Females of childbearing age will be tested for pregnancy and

asked to sign a commitment form to be on 2 forms of acceptable contraceptives for duration of study. A physical examination will also be done. Blood samples will be taken in order to evaluate HbA1c, CBC, CMP and liver and kidney functions and pregnancy status. Patients meeting all the inclusion and exclusion criteria based on all screening tests will be enrolled in the study.

- N/A:** There is no screening as part of this protocol.

9.0 Recruitment Methods

- N/A:** This is a records review only, and subjects will not be recruited. NOTE: If you select this option, please make sure that all records review procedures and inclusion/exclusion screening are adequately described in other sections.

9.1 *Describe when, where, and how potential subjects will be recruited.*

NOTE: Recruitment refers to how you are identifying potential participants and introducing them to the study. Include specific methods you will use (e.g. searching charts for specific ICD code numbers, Research Participant Groups, posted advertisements, etc.).

Response: Potential participants will be identified by prescreening clinical charts, patient doctor interaction at the time of their visits. In addition patients will be recruited through advertisements , Buffalo Research Registry and researchmatch.org. Diabetes Endocrinology Center of WNY Locations include:

1. [name]
2. [name]
3. [name]

The study clinical team will evaluate their clinic patients for possible participation in this study according to the inclusion and exclusion criteria at the Diabetes and Endocrinology Center of WNY. Patients that may qualify are asked during their clinic visits if they are interested in participating in research. Patients that agree will be referred to the research team for further eligibility evaluation. If these patients meeting the inclusion and exclusion criteria based on preliminary phone evaluation will be scheduled for a screening visit.

Facebook and Craigslist will be used for recruitment. The approved advertisement will be posted on the main advertising board at Erie County Medical Center. A generic flyer will be utilized also for recruiting.

9.2 *Describe how you will protect the privacy interests of prospective subjects during the recruitment process.*

NOTE: Privacy refers to an individual's right to control access to him or herself.

Response: Patient charts will be screened according to the study inclusion and exclusion criteria by our trained clinical staff and physicians. If the patient qualifies and is of consenting age, the physicians will speak to them about their interests in participating in research. If the patient agrees, their information will be given to the research coordinator to be contacted for further evaluation. Potential

subjects recruited from advertisement will call the research team for more information regarding participating in research. All personal information will be kept confidential and locked in the coordinator office.

9.3 Identify any materials that will be used to recruit subjects.

NOTE: Examples include scripts for telephone calls, in person announcements / presentations, email invitations.

 *For advertisements, include the final copy of printed advertisements with your submission. When advertisements are taped for broadcast, attach the final audio/video tape. NOTE: You may submit the wording of the advertisement prior to taping to ensure there will be no IRB-required revisions, provided the IRB also reviews and approves the final version.*

Response: In addition to screening clinical charts, participations will be identified through; advertisement, Buffalo Research Registry, researchmatch.org, craigslist.com, and facebook

10.0 Procedures Involved

10.1 Provide a description of **all research procedures or activities** being performed and when they are performed once a subject is screened and determined to be eligible. Provide as much detail as possible.

NOTE: This should serve as a blueprint for your study and include enough detail so that another investigator could pick up your protocol and replicate the research. For studies that have multiple or complex visits or procedures, consider the addition of a schedule of events table in in your response.

Response:

Visit 1 (week 0):

Qualifying subjects will be asked to come for the visit in a fasting state (10-12 hr fasting), vitals will be done and safety labs for CBC, CMP, HbA1C, kidney function tests will be drawn and 24hr urine will be collected. Blood samples (30ml) will be collected for research endpoints. Training on administrating study drug and information about side effects and how to report any adverse events will be discussed with patients. One of the treatment arms will be administered to the patient (placebo or Exenatide extended release in a randomized fashion) and enough drug supply for 13+2 weeks will be dispensed. Other diabetes medications will be reviewed and any standard of care adjustments will be made. A 24hr urine collection container will be dispensed and patients will be instructed to come back after 13 weeks.

Visits 2, 3 and 4 (Weeks 13, 26 and 39):

Patients will come to this visit in the fasting state. Physical exam (only on visit 3) and vitals will be performed, safety labs for CBC, CMP, HbA1c, kidney function tests will be drawn and 24hr urine collected. Blood samples (30ml) will be collected for research endpoints. Other diabetes medications will be reviewed and any standard of care adjustments will be made. Study medication use compliance will be assessed and drug supply for 13+2 weeks will be dispensed. A 24hr urine collection container will be dispensed and patients will be instructed to come back after 13 weeks.

Visit 5 (Week 52): Patients will come to this visit in the fasting state. Physical exam and vitals will be performed, safety labs for CBC, CMP, HbA1c, kidney function tests will be drawn and 24hr urine collected. Blood samples (30ml) will be collected for research endpoints. Other diabetes medications will be reviewed and any standard of care adjustments will be made. Patient will be discharged from the study after the final safety phone call at week 56.

Phone call will also be made at weeks 2, 8, 18, 34 and 46 weeks to inforce compliance and to ensure safety. Patients will also be instructed to call if they develop unexpected symptoms.

LABORATORY PROCEDURES

1. **MNC isolation:** Blood samples (30-40ml) is collected in Na-EDTA and carefully layered on Lympholyte medium (Cedarlane Laboratories, Hornby, ON) according to manufacturer's instructions. Samples are centrifuged and two bands separate out at the top of the RBC pellet. The MNC band was harvested and washed twice with Hank's balanced salt solution (HBSS). This method provides yields greater than 95% MNC preparation.
2. **ROS generation measurement by chemiluminescence:** Five hundred μ L of MNC (2×10^5 cells) are delivered into a Chronolog LumiAggregometer cuvette. Luminol is then added, followed by 1.0 μ L of 10 mM formylmethionyl leucinyl phenylalanine (fMLP). Chemiluminescence is recorded for 15 minutes. In this assay system, the release of superoxide radical as measured by chemiluminescence, has been shown to be linearly correlated with that measured by the ferricytochrome C method. The interassay coefficient of variation of this assay is 8 %. We have further established that the biological variation in reactive oxygen species generation in normal subjects is approximately 6 % for readings obtained 1 to 2 weeks apart. Similarly, the variation in reactive oxygen species generation in the obese over a period of 1 to 2 weeks is less than 8 %.
3. **Quantification of p47^{phox}, Keap-1, NQO-1, GST-1P, HO-1 and SMADs 2-4 expression:** The mRNA expression is measured in MNC by RT-PCR: Total RNA was isolated using commercially available RNAqueous®-4PCR Kit (Ambion, Austin, TX). One μ g of total RNA is reverse transcribed using Advantage RT-for-PCR Kit (Clontech, CA). Real Time RT-PCR was performed using Stratagene Mx3000P QPCR System (La Jolla, CA), Sybergreen master mix (Qiagen, CA) and gene specific primers ([name]). All values were normalized to the expression of a group of housekeeping genes including actin, ubiquitin C and cyclophilin A.
4. **Western blotting:** MNC total cell lysates are prepared and proteins separated by SDS-PAGE and then transferred to PVDF membrane. Polyclonal or monoclonal antibodies against p47^{phox}, Keap-1, Nrf-2, SMADs and NQO-1 (Abcam, Cambridge, MA) and actin (Santa Cruz Biotechnology, CA) will be used. Densitometry is performed using molecular analyst software (Biorad, CA) and all values are corrected for loading with actin.

5. **Nrf-2 DNA binding:** Nuclear Nrf-2 DNA binding activity will be measured by EMSA. Nuclear extract is prepared from freshly tissues by NE-PER® Nuclear Extraction kit (Pierce Biotechnology, Rockford, IL). The specificity of the bands is confirmed by supershifting these bands with specific antibodies against Nrf-2 (Santa Cruz Biotechnology, CA) and by competition with cold oligonucleotides. DNA binding activity of Nrf-2 will be adjusted to Oct-1 DNA binding activity to correct for technical variables.
6. **Plasma measurements:** Glucose levels are measured in plasma by YSI 2300 STAT Plus glucose analyzer (Yellow Springs, Ohio). ELISA kits will be used to measure insulin (Millipore, MA), TGF-b1, CTGF, TIMPs, PAI-1 (R&D Systems), type I and IV collagen and fibronectin (fibronectin EDA). HbA1c, serum creatinine and cystatin C will measured by standard assays by Quest Diagnostic Labs.
7. **Urinary measurements:** Albuminuria, creatinine, creatinine clearance, GFR will measured from 24hr urine collection by standard assays by Quest Diagnostic Labs.
8. **15-isoprostane F_{2t}** (also known as 8-epi-PGF2 α or 8-iso-PGF2 α) in urine samples will be measured by an ELISA kit from Oxford Biomedical Research (Oxford, MI).

10.2 Describe what data will be collected.

NOTE: For studies with multiple data collection points or long-term follow up, consider the addition of a schedule or table in your response.

Response:

The study investigations include evaluation of the effects of 1-year treatment with Exenatide extended release or placebo on progression of albuminuria and related kidney function measures in T2DM patients with established micro- or macroalbuminuria. Qualified patients will come fasting to the research center. Review of study procedures and vitals will be performed. Basal blood and 24-urine samples will be obtained. Patients will be randomized (in 2:1 ratio) to receive either Exenatide extended release or placebo for 1 year. Plasma and mononuclear cell (MNC) fractions will be prepared from the blood samples. Additional fasting blood and 24hr urine samples will be collected every 13 \pm 2 weeks (3, 6, 9 and 12 months) for a total of 5 study visits. Measurements of albuminuria, creatinine, creatinine clearance, GFR, isoprostanes and cystatin C following 1-year treatment with Exenatide extended release or placebo will be done on all urine samples collected before and at 3, 6, 9 and 12 months following treatment with Exenatide extended release or placebo. HbA1c, CBC, CMP, TGF β , type I and IV collagen, CTGF, PAI-1, TIMP-1 and 2 and fibronectin EDA levels will be measured in all plasma samples collected while the expression of SMAD3, SMAD4, NQO-1, GST-1P and HO-1, Nrf-2/keap-1 system activation, p47^{phox} levels and ROS generation will be done in all MNC samples collected before and at 13, 26, 39 and 62 weeks following treatment with Exenatide extended release or placebo.

Visit #	Screening	1	2	3	4	5
Weeks #	<-4	0	13 \pm 2	26 \pm 2	39 \pm 2	52 \pm 2
Medical History	X					
Physical exam	X			X		X

CBC/CMP/kidney function	X	X	X	X	X	X
Vitals and BP	X	X	X	X	X	X
Pregnancy test	X		X	X	X	X
HbA1c	X	X	X	X	X	X
MNC endpoints		X	X	X	X	X
Plasma mediators endpoints		X	X	X	X	X
Urinary endpoints		X	X	X	X	X
Other diabetes medications review and adjustments		X	X	X	X	X

 10.3 List any instruments or measurement tools used to collect data (e.g. questionnaire, interview guide, validated instrument, data collection form).

Include copies of these documents with your submission.

Response: Source documents will be used to collect patient information. Food and glucose measurement diaries will be also reviewed for medication adjustment.

10.4 Describe any source records that will be used to collect data about subjects (e.g. school records, electronic medical records).

Response: electronic medical records and research files.

10.5 Indicate whether or not **individual** subject results, such as results of investigational diagnostic tests, genetic tests, or incidental findings will be shared with subjects or others (e.g., the subject's primary care physician) and if so, describe how these will be shared.

Response: Individual participant lab results will be disclosed to the participant upon their request. If the participant requests documentation be shared with another physician, physician office or hospital the participant must come to the research center to collect said documentation or the documentation can be mailed to their given home address.

10.6 Indicate whether or not **study** results will be shared with subjects or others, and if so, describe how these will be shared.

Response: Not Applicable. Study results will not be shared with the subjects. However, unidentifiable study results could be published in the form of a manuscript or abstract and will be reported to Astra Zeneca and to clinicaltrials.gov

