6.0 Inclusion and Exclusion Criteria

6.1 *Describe the criteria that define who will be **included** in your final study*

6.2 *sample.*

NOTE: This may be done in bullet point fashion.

Response:

Inclusion Criteria

- Type 2 Diabetes for at least 1 year.
- Microalbuminuria for at least 6 months (UACR: 30-300 mg/g)
- Macroalbuminuria for at least 6 months (UACR: >300 mg/g)
- HbA1c of $\leq 10\%$
- Ages 18-65 years (inclusive of ages 18 and 65)
- On ARBs/ACEi for at >3months

6.3 *Describe the criteria that define who will be **excluded** from your final study sample.*

NOTE: This may be done in bullet point fashion.

Response:

Exclusion Criteria

- Use of GLP-1 Receptor agonists or SGLT-2 inhibitors therapy in the last 3 months
- History or risk for pancreatitis (e.g., history of gallstones, alcohol abuse, and hypertriglyceridemia)
- Coronary event or procedure (myocardial infarction, unstable angina, coronary artery bypass, surgery or coronary angioplasty) in the previous 3 months
- Hepatic disease: Severe hepatic insufficiency and/or significant abnormal liver function defined as:
 1. Aspartate aminotransferase (AST) >3x upper limit of normal (ULN) and/or alanine aminotransferase (ALT) >3x ULN
 2. Total bilirubin >2.0 mg/dL (34.2 μ mol/L)
 3. Positive serologic evidence of current infectious liver disease including Hepatitis B viral antibody IGM, Hepatitis B surface antigen and Hepatitis C virus antibody
 4. Liver function tests more than 3 times the upper limit of normal
- *Renal impairment (serum eGFR <30 ml/min)*
- HIV
- Inability to give informed consent
- History of gastroparesis
- History of medullary thyroid carcinoma or MEN 2 syndrome
- Alcoholism
- Hypertriglyceridemia (>500 mg/dl).
- Any other life-threatening, non-cardiac disease
- Uncontrolled hypertension (BP > 160/100 mm of Hg)
- Congestive Heart Failure class III or IV
- Use of an investigational agent or therapeutic regimen within 30 days of study
- Participation in any other concurrent clinical trial
- Pregnant or breastfeeding patients or females of childbearing age not on 2 forms of acceptable contraceptives.

6.4 *Indicate specifically whether you will include any of the following special populations in your study using the checkboxes below.*

NOTE: Members of special populations may not be targeted for enrollment in your study unless you indicate this in your inclusion criteria.

Response: NA

- Adults unable to consent

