18.10 B. How will the specimens be transported?

Response: Fresh samples collected for screening and safety will be transported by Quest Diagnostics courier at ambient temperature and according to Quest Diagnostics instructions. Frozen samples that are transported will be done so using dry ice in a properly labeled Styrofoam container by the laboratory technician.

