Response Safety data (vitals, CBC, CMP, urinary markers) will be collected at screening, during and at end of the study. Injection site reactions and hypoglycemia data will be monitored and collected at every visit. Physical examination will be performed at 26 and 52 weeks visits and safety assessments performed. Pregnancy results and contraceptive adherence plan (if applicable) will be reviewed at screening, 16 and 39 and 52 weeks.

19.3 Describe any safety endpoints.

Response: N/A.

19.4 Describe how the safety information will be collected (e.g., with case report forms, at study visits, by telephone calls with participants).

Response: The safety information will be collected at the time of the participants visit, and or during telephone calls with the participant using source documents.

19.5 Describe the frequency of safety data collection.

Response: The data collection will be done at all study visits which will be at intervals of either one or two weeks depending on the number of study visit. The patients, however, will be asked to report any adverse event or safety related information via phone as soon as it occurs and it will be reviewed the same day.

19.6 Describe who will review the safety data.

Response: The principal investigator [name], PhD and co-investigators, [name] and [name] will review the data at the completion of all visits by each subject and every 3 months to assess the safety and any potential risks to the participants.

19.7 Describe the frequency or periodicity of review of cumulative safety data.

Response: Every 3 months, [name], [name] and [name] will assess the safety and any potential risks to the participants. Safety data (vitals, CBC, CMP, urinary markers) will be collected at screening, during and at end of the study. Injection site reactions and hypoglycemia data will be monitored and collected at every visit. Physical examination will be performed at 26 and 52 weeks visits and safety assessments performed. Pregnancy (if applicable) will be tested at screening, 16 and 39 and 52 weeks. Oral anti-hyperglycemic agents and/or insulin dose titration will be done to avoid hypoglycemia. Phone calls will be made for safety and compliance follow-up at least 6 time during the study. The patients, however, will be instructed to report any adverse event or safety related information via phone as soon as it occurs. All safety data will be reviewed by the PI or sub-investigators within 1-2 days of collection.

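### No pregnancy test is scheduled at Visit 1, the screening heading `<-4` weeks is ambiguous, and the first dose is not conditional on any laboratory result drawn that day

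*Combined protocol and SAP*

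**What the plan says.** **Eligibility.** Section 6.3 excludes "Pregnant or breastfeeding patients or females of childbearing age not on 2 forms of acceptable contraceptives". Section 21.4 adds that pregnant participants will not be enrolled, and that anyone who becomes pregnant will be withdrawn at once. At screening (Section 8.1), "Blood samples will be taken in order to evaluate HbA1c, CBC, CMP and liver and kidney functions and pregnancy status". The entry decision follows from that visit: "Patients meeting all the inclusion and exclusion criteria based on all screening tests will be enrolled in the study".

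**Timing of screening.** The visit table in Section 10.2 heads the screening column `<-4` weeks. Visits 2 to 5 each carry a window of ±2 weeks; screening carries none. No other section gives a screening window or a maximum age for screening results. Section 11.2 gives participation as 52 weeks and does not mention screening.

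**Visit 1.** Section 10.1 states that "vitals will be done and safety labs for CBC, CMP, HbA1C, kidney function tests will be drawn and 24hr urine will be collected". At the same visit, "One of the treatment arms will be administered to the patient". No pregnancy test is listed. The review of other diabetes medications comes after the dose in the text and is described as being for standard-of-care adjustments.

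**Pregnancy tests.** The table row reads "Pregnancy test X X X X X": the marks stand under screening and Visits 2, 3, 4 and 5, and the Visit 1 cell is empty. Section 19.7 says "Pregnancy (if applicable) will be tested at screening, 16 and 39 and 52 weeks". Section 21.2 says the same, and Section 19.2 gives the same weeks for review of pregnancy results.

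**Handling of results.** Section 18.10 states that "Fresh samples collected for screening and safety will be transported by Quest Diagnostics courier at ambient temperature". Section 19.7 has safety data reviewed within 1-2 days of collection.

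**The concern.** An exclusion criterion protects the patient, and defines the study population, only if it is known to be satisfied when treatment starts. Here the only pregnancy result before the first dose comes from a screening visit whose date is not clearly bounded. A woman who conceives between screening and week 0 meets an exclusion in Section 6.3, yet a site following the plan to the letter would randomise and dose her.

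The laboratory criteria (HbA1c, liver tests, eGFR) have a related weakness. They are either redrawn at Visit 1 or covered by panels redrawn then, so newer values will exist. Nothing requires anyone to see those values before the dose, and the samples go to an outside laboratory.

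What is at stake is mainly participant safety and the plan's ability to show that its own criteria were met. A secondary consequence is that a patient randomised while ineligible may then be withdrawn (Sections 20.1 and 21.4) from a trial with 15 placebo patients per albuminuria stratum.

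**Working it through.** The plan states no figure to reproduce. The check compares the sections and then works out the intervals they imply.

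**1. Is there a week-0 pregnancy test anywhere?**

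| Place | Pregnancy test times | Week 0? |
|---|---|---|
| 8.1 Screening | screening | no |
| 10.1 Visit 1 text | none listed | no |
| 10.2 table | screening, 13, 26, 39, 52 | blank |
| 19.2, 19.7 | screening, 16, 39, 52 | no |
| 21.2 | screening, 16, 39, 52 | no |

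The sections agree that week 0 is omitted. They disagree about later tests: the table has four and the text three, and only weeks 39 and 52 match. Visit 2 spans 13 - 2 = 11 to 13 + 2 = 15, and Visit 3 spans 26 - 2 = 24 to 26 + 2 = 28. Week 16 therefore falls in no visit window. It is not one of the phone-call weeks in Section 10.1 either (2, 8, 18, 34, 46, and a final call at 56).

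**2. Age of the screening result at first dose**

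- Reading A, within 4 weeks: 0 to 4 weeks.
- Reading B, literally earlier than week -4: more than 4 weeks, no maximum.

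**3. Interval from the screening test to the next test** = (weeks from screening to week 0) + (week of next test)

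| | Next test at Visit 2 (weeks 11-15) | Next test at week 16 |
|---|---|---|
| Reading A | 0 + 11 = 11 to 4 + 15 = 19 weeks | 0 + 16 = 16 to 4 + 16 = 20 weeks |
| Reading B | more than 4 + 11 = 15 weeks, no maximum | more than 4 + 16 = 20 weeks, no maximum |

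Time on study drug before the first on-treatment test does not depend on the reading: 11 to 15 weeks by the table, 16 by Sections 19 and 21.

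**4. Can Visit 1 results act as a check?** Vitals and blood pressure can, because they are listed before dosing and known at once. The laboratory tests cannot, as written: they are drawn at the dosing visit, sent out by courier and reviewed within 1-2 days, and no sentence holds the dose until they are back. The diabetes-medication review could serve for the GLP-1RA/SGLT-2 inhibitor exclusion, but it is not tied to eligibility and is listed after the dose.

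**The case against.** The strongest reply is that `<-4` is ordinary shorthand for less than four weeks before week 0. The literal reading would forbid screening in the last four weeks, and nothing else in the protocol suggests that intention. This is persuasive. A reader might infer from the heading that the first dose can rest on eligibility results of any age. The documents do not support that as a flat statement, because it holds on only one of two readings and that is the less plausible one. What stands is that the heading is ambiguous, and that on either reading week 0 has no pregnancy test.

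A reader might also infer that nothing is re-checked at Visit 1. That is wrong. Blood pressure is measured again and other diabetes medications are reviewed.

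It is tempting to use the pilot data in Section 3.1 to argue that eGFR could fall below 30 between screening and dosing. The steepest decline there is 30.3 / 3.6 = 8.4 ml/min per year, or 0.70 per month. It comes from nine macroalbuminuric non-users (30.3 ± 23.3, mean baseline 88.5), and the 3.6 years is the mean follow-up of all 191 non-users. Other albuminuric subgroups give slower rates:

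- macro users: (76.5 - 70.1) / 2.3 / 12 = 0.23 per month
- micro users: 8.6 / 2.3 / 12 = 0.31 per month
- micro non-users: 12.1 / 3.6 / 12 = 0.28 per month

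Even at 0.70 per month, four weeks costs 0.70 × 12 × 4/52 = 0.65 ml/min. The pilot data do not make this a material risk.

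Finally, there are safeguards: women of childbearing age sign a commitment to two contraceptive methods (8.1), safety calls take place at weeks 2 and 8 (10.1), and pregnancy leads to immediate withdrawal (21.4). These lower the risk. They do not establish pregnancy status at the first dose.

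**Conclusion.** The point holds as a gap in eligibility control and a contradiction in the schedule. Followed as written, the plan can give a first dose to a patient who meets its own pregnancy exclusion, and the next scheduled test comes 11 to 15 or 16 weeks later, depending on which section is followed. The gap between the screening test and the next is 11 to 19 weeks (16 to 20 using week 16) if `<-4` means within 4 weeks. It is more than 15 weeks (more than 20) with no maximum on the literal reading. The first set assumes the more plausible reading, which the documents do not confirm.

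How many patients this would affect cannot be estimated, since the documents do not give the expected share of women of childbearing age. A reader might infer a threat to power or to the primary comparison; no such effect is shown. The sample size, alpha and mixed model do not depend on this point, and removal under Section 20.1 is at the investigator's discretion, apart from the withdrawal on pregnancy stated in Section 21.4.

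**What to change.** 1. Replace `<-4` in the Section 10.2 table with a window that has both ends stated, and say what happens to a patient who exceeds it.
2. Reconcile Sections 6.3, 8.1, 10.1, 10.2, 19.2, 19.7, 21.2 and 21.4 so that pregnancy status and the other laboratory eligibility results are confirmed within a stated time before randomisation. Say which results must be in hand before the first dose. The length of that time is for the sponsor to set.
3. Make the later pregnancy-test weeks agree between the table (13, 26, 39, 52) and Sections 19 and 21 (16, 39, 52), and tie each to a visit that exists. Which set is intended is for the sponsor to say.
4. In Section 10.1, place the existing Visit 1 diabetes-medication review before dosing and state that it confirms the GLP-1RA/SGLT-2 inhibitor exclusion as of week 0.

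The cost is one table heading, a few sentences, possibly one inexpensive additional test for some women, and occasional repeat screening laboratory work. No change to the sample size or analysis is needed.
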